## 8.6 Efficacy analyses

Responder-type endpoints (ACR20, ACR50, ACR70) will be summarized with response rates and 95% confident intervals (CI) by treatment group and visit.

Observed and change from baseline in continuous endpoints (tender joint counts, swollen joint counts, PGA of disease activity, PtGA of disease activity, patient’s pain assessment, HAQ-DI, acute-phase hsCRP, ESR, SF-36) will be summarized by treatment group and visit with n, mean, SD, median, and range. No statistical tests will be performed.

At the start of the long-term extension study, each subject will continue to receive the same dose

# Statistical Analysis Plan (SAP)

regimen received at the end of the parent study. A decision to remove one or more treatment arms from the long-term extension study may occur as information from parent studies becomes available, and subjects in this extension study may be switched to selected dose regimens at that time. The subjects will be summarized based on the actual treatment received at the beginning of the extension study.

All analyses will be performed using ASaT population.

## 8.7 Safety analyses

Safety analyses will be conducted on the ASaT population and will be performed for all safety variables specified below.

The subjects will be summarized based on the actual treatment received at the beginning of the extension study.

The safety analyses of changes from baseline to a specific time point in safety variables (e.g., laboratory parameters, vital signs, and ECG) will only include subjects from ASaT who have data available for both the baseline and the time point under consideration unless otherwise specified. Where relevant, temporal relationships to parent study baseline will be described.

No statistical tests will be performed.

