## Statistical Analysis Plan (SAP)

A decision to remove 1 or more treatment arms from the long-term extension study may occur as information from the parent study becomes available. Subjects already enrolled in the long-term extension study may be switched to selected dose regimens for continued evaluation at that time. This decision is anticipated to occur approximately 1 year after the start of the long-term study.

When all subjects have completed the PsA parent Phase 2 study, the blind will no longer need to be maintained for that cohort, and this long-term extension study will have the option to become open-label for those subjects. At that time, the dummy placebo administration will be removed. Note: the timing of switch to an open-label design may differ across the cohorts of subjects entered, dependent on the parent study. If other studies are also included in the long-term extension study, similar considerations for maintenance of blind will be necessary. Those subjects will be entered as separate cohorts and procedures such as continued double-dummy dosing regimens will be utilized, even after other parent Phase 2 cohorts have the option to switch to open-label.

In PsA Phase 2 study [CLR\_16\_23 PsA study], both tildrakizumab, 200 mg q12 weeks and tildrakizumab 100 mg, q12 weeks provided similar efficacies in the ACR20, ACR50, and ACR70 at Week 24. The lowest dose of 20 mg q12 weeks, did not demonstrate superiority over placebo in ACR70 and had numerically lowest ACR50 response rate among the active doses tested. The highest dose of tildrakizumab 200 mg q4 weeks, did not provide significant benefit over tildrakizumab 200 mg, q12 weeks. Therefore, the dose regimen of tildrakizumab 100 mg, q12 weeks is chosen for the long-term extension study going forward.

After all subjects switch to receive 100 mg tildrakizumab Q12W in an open-label fashion, there will be no efficacy assessments and the primary focus is the long-term safety of tildrakizumab.

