# Statistical Analysis Plan (SAP)

## 8 STATISTICAL METHODS

### 8.1 General Statistical Conventions

All statistical procedures will be completed using SAS version 9.4 or higher.

Continuous variables will be summarized using descriptive statistics, including number of subjects (n), mean, median, standard deviation (SD), minimum and maximum. One additional decimal point for mean and median and 2 additional decimal points for SD will be used.

For categorical variables, summaries will include counts of subjects and percentages. Percentages will be rounded to one decimal place.

Two-sided 95% confidence intervals (CI) will be provided when relevant.

For summary purposes, baseline will be defined as the last available value prior to the date of first IMP administration in parent study.

For reporting purpose, summary tables for efficacy variables and safety variables will be displayed by nominal visit as appropriate. Unscheduled assessments will not be included in the summary tables, but will be in data listings.

All subject data, including those derived, will be presented in individual subject data listings. Unless otherwise stated, unscheduled visit results will be included in date/time chronological order, within patient listings only. All listings will be sorted by treatment group, subject number, date/time and visit. The treatment group as well as patient's sex and age will be stated on each listing. Unless otherwise stated, data listings will be based on ASaT population.

The treatment groups will be displayed in the format below in tables:

- 200 mg Tildrakizumab q4wk
- 200 mg Tildrakizumab q12wk
- 100 mg Tildrakizumab q12wk

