## 8.5 Extent of exposure

### 8.5.1 Treatment Duration

Duration of study drug exposure (in days) will be calculated as: last dose date – first dose date + 1 day, regardless of study drug interruption.

Study drug exposure will be summarised by treatment group using descriptive statistics.

Exposure to randomized study drug will also be categorised in intervals  $\leq 3$  months ( $<91$  days), 3-6 months (91-180 days), 6-12 months (181-365 days), 1-2 years (366-730 days), 2-3 years (731-1095 days),  $>3$  years ( $>1095$  days) and summarized by treatment group.

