# Statistical Analysis Plan (SAP)

- TEAEs leading to study discontinuation
- Serious TEAEs
- TEAEs leading to death.

An overall summary for the categories above will be presented by treatment group and overall.

Due to the various durations of exposure to a treatment, the exposure-adjusted AE incidence rate (per 100 subject-years) will be summarized by treatment group. The incidence of AEs will be presented by system organ class and PT. In addition, all TEAEs will be summarized by SOC, PT and treatment group using frequency counts and percentages (i.e., number and percentage of subjects with an event).

Where a subject has the same adverse event, based on preferred terminology, reported multiple times in the study, the subject will only be counted once at the preferred terminology level in adverse event frequency tables.

Where a subject has multiple adverse events within the same system organ class in the study, the subject will only be counted once at the system organ class level in adverse event frequency tables.

When reporting adverse events by intensity, in addition to providing a summary table based on the event selection criteria detailed above, summary table will also be provided based on the most intense event - independent of relationship to study treatment.

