## 8.8 Other analysis

### 8.8.1 Analysis of Pharmacokinetic Endpoints

Plasma tildrakizumab concentration data will be listed by individual subject and summarized by time and tildrakizumab dose group. The subjects will be summarized based on the ASaT population with the actual treatment received at the beginning of the extension study.

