### 8.8.2 ADA to Tildrakizumab

For each subject, tildrakizumab serum concentrations and ADA sample results are matched to actual sampling times and treatment. Subjects are grouped based on the actual treatment received. Subjects have baseline samples taken prior to dosing to assess for any preexisting immune response that may be detected by the ADA assays. Subjects are considered positive if at least one pre-treatment or post-dose sample is positive at any time. Positive subjects are subsequently categorized into treatment-emergent positive if the positive sample occurs following treatment with tildrakizumab or non-treatment emergent positive if the subject has an immune response present at baseline and the response is not boosted following treatment.

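### The final by-group safety and PK tables keep subjects in their entry-regimen column after the switch, so 100 mg Q12W data appear as 200 mg data

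*SAP*

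**What the plan says.** **Grouping.** SAP 8.7 states for safety: "The subjects will be summarized based on the actual treatment received at the beginning of the extension study". SAP 8.8.1 repeats it for PK: "The subjects will be summarized based on the ASaT population with the actual treatment received at the beginning of the extension study". SAP 8.1 says "The treatment groups will be displayed in the format below in tables" and lists 200 mg q4wk, 200 mg q12wk and 100 mg q12wk. There is no post-switch or sequence column.

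**Exposure and rates.** SAP 8.5.1 counts exposure from first to last dose without a split, and "Study drug exposure will be summarised by treatment group using descriptive statistics". Its categories run past 3 years. In SAP 8.7.1, "the exposure-adjusted AE incidence rate (per 100 subject-years) will be summarized by treatment group".

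**Switch.** SAP 3.1, 3.2.2 and 3.3 keep subjects on their parent-study regimen for at least 52 weeks of blinded dosing in the extension. After the last subject's Week 52 visit, all migrate to open-label 100 mg Q12W. SAP 8.6 foresees that "subjects in this extension study may be switched to selected dose regimens at that time", and then adopts the entry-regimen rule.

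**Protocol.** Section 12.3.1 groups safety data by the treatment received at particular time points, where that applies. Section 12.3.2 groups PK by the treatment received at the visit, with no qualifier. SAP section 1 promises to identify substantial differences from the protocol; SAP section 10 reads as not applicable.

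**ADA.** SAP 8.8.2 says "Subjects are grouped based on the actual treatment received", while its Table 2 gives each subject a single status.

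**The concern.** Long-term safety is the primary objective (protocol 8.1, SAP 2.1), and the by-group AE tables with rates per 100 subject-years are its main display. Entry-regimen grouping does little harm to efficacy: SAP 3.1 says that once all have switched "there will be no efficacy assessments and the primary focus is the long-term safety of tildrakizumab". Safety and PK data, however, continue to Week 208.

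The study is descriptive and has no dose-comparison objective, so no test is at risk. What is at risk is the meaning of the columns. Rates headed 200 mg would be diluted with 100 mg Q12W time. The record of 100 mg Q12W, the regimen kept for the rest of the study, would be scattered over three columns. The overall column is correctly labelled but mixes regimens, so it gives no 100 mg Q12W rate. The AE listing in protocol 12.3.1 carries treatment at onset, so events can be re-attributed by hand, but a listing supplies no denominators.

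**Working it through.** The plan gives no power or event figure to reproduce: N is a rollover count. The check is a reading of the rules, followed by the size of the effect.

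**1. Does the rule reach post-switch data?** Yes. Nothing in the SAP censors at the switch, splits periods or limits the tables to the blinded phase, and the exposure categories extend beyond 3 years.

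**2. Which entry regimen applies?** The documents conflict.
- 100 mg Q12W from extension Week 0: protocol synopsis (flow-diagram note 1, Test Product), Figure 9-1 note 1, 9.1.3.1.2, part of 10.2.4; SAP 3.1 figure note 1. Protocol 9.1.1 and 10.1.1 place it after parent Week 52. On these readings nothing is mislabelled.
- Parent regimen first: protocol 9.1.3, 9.2, the rest of 10.2.4; SAP 3.1 text, 3.2.2 and 3.3.
- A change during the extension: the synopsis Methodology, which ties 100 mg to the amendment, and the closing note of SAP 2.3.

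If everyone entered on 100 mg Q12W, the entry rule would leave both 200 mg columns in SAP 8.1 empty. The SAP's tables therefore presuppose a later switch.

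**3. Share of a 200 mg completer's column time spent on 100 mg Q12W.** With exposure counted to the last dose at Week 200 and a switch at week S, f = (200 − S)/200. The apparent rate ratio for a true ratio of 2.0 is 2(1 − f) + f = 2 − f, ignoring carry-over.

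| S | f | Apparent ratio |
|---|---|---|
| 52 (last entrant only) | 148/200 = 0.74 | 1.26 |
| 78 (mean switch if entry is uniform over 52 weeks) | 122/200 = 0.61 | 1.39 |
| 104 | 96/200 = 0.48 | 1.52 |

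**4. With an assumed 20% annual dropout.** λ = −ln(0.8) = 0.2231. Person-time to week w is (1 − exp(−λw/52))/λ, which gives 0.896, 1.275, 1.613 and 2.582 years at Weeks 52, 78, 104 and 200.
- S = 52: 1 − 0.896/2.582 = 0.653, ratio 1.35
- S = 78: 1 − 1.275/2.582 = 0.506, ratio 1.49
- S = 104: 1 − 1.613/2.582 = 0.375, ratio 1.62

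At 10% dropout the shares are 0.700, 0.561 and 0.430; at 30% they are 0.598, 0.445 and 0.317.

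**5. Are these switch weeks plausible?** Planned start was June 2018 (synopsis) and the parent lock was 05 Nov 2019 (protocol 7.1), 70.4 to 74.6 weeks apart. If the last entry was 20 weeks before lock (the wash-out length), the entry window is 50.4 to 54.6 weeks. With uniform entry, mean switch = 52 + window/2: Week 77 to 79 for the shorter window (share 60–61%) or Week 87 to 89 for the longer (55–56%). The first entrant would switch at 52 + window, about Week 102 to 127. A migration lag of up to 12 weeks lowers a share by up to 12/200 = 6 points.

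**6. PK.** Moving from 200 mg Q4W (50 mg/week) to 100 mg Q12W (100/12 = 8.3 mg/week) is a sixfold fall in dose rate. The amended schedule samples at Weeks 20, 56, 104, 152, 200 and 208. For a subject switching at Week 56, the last four of these six would sit under 200 mg q4wk, where a regimen change could be read as falling exposure.

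**The case against.** The entry rule is deliberate. SAP 8.6 foresees the switch and then chooses it, SAP section 1 says the SAP supersedes the protocol's statistical considerations, and protocol 12.3.1 is qualified. A column defined by entry regimen is correct on its own definition. That is fair as far as it goes, but the SAP 8.1 headings name the regimen and not the entry group, protocol 12.3.2 carries no qualifier, and section 10 is silent.

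The Week 52 interim (SAP 8.9) has the same trigger as the migration, so its by-group tables should hold nearly all 200 mg exposure unmixed, unless the data cut is earlier. This stands: those tables are not mislabelled. They do not repair the final tables or supply a 100 mg Q12W rate.

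Laboratory, ECG and PK tables are by visit, so only Weeks 56 and 104 would mix regimens. But that makes the later rows (Weeks 152 to 208) of the 200 mg columns entirely 100 mg Q12W data.

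For ADA, SAP 8.8.2 matches samples to sampling time and treatment. That settles samples, but a switcher's single status still has no defined group.

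By-period columns have their own attribution problem. Baseline is the parent-study value (SAP 8.1), so a late change shown under 100 mg includes earlier time on 200 mg, and so do cumulative-exposure events such as malignancy. This stands, and is a reason to keep both sets of tables.

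The premise is conditional, and SAP 3.3 also describes each arm as running to Week 200, so original and amended design text are mixed. The magnitudes rest on assumptions, and protocol 7.2.1 reports no dose-related toxicities to date.

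**Conclusion.** The concern holds, conditional on the SAP's own design of parent regimen first and a later switch. Under that design the final 200 mg columns for safety and PK contain 100 mg Q12W data, contrary to protocol 12.3.2 outright and to 12.3.1 in substance, with no declared change. Subjects entering on 100 mg Q12W, the overall column and the Week 52 interim are unaffected.

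Roughly half to three-quarters of a 200 mg completer's column time would be misattributed, and about 38% to 65% with 20% annual dropout. Switch weeks, uniform entry, dropout, a study start as planned and the November 2019 lock being the final one are all assumptions. The rate ratio of 2.0 shows the size of the dilution and is not an expected effect. The point should be corrected before the final analysis; it does not threaten a formal inference, because there is none.

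**What to change.** - In SAP 8.5.1, 8.7 and 8.8.1, with matching columns in 8.1, split each subject's exposure at the first open-label 100 mg Q12W dose after the switch. Assign AEs by regimen at onset, subject-years by regimen, and laboratory, vital-sign, ECG and PK data by regimen at the visit.
- Add one column pooling all 100 mg Q12W exposure. Keep the entry-regimen tables as supportive, labelled as such.
- In SAP 8.8.2, state which group a switcher's single ADA status belongs to.
- If early post-switch AEs are flagged for carry-over, justify the window from PK.
- List any remaining difference from protocol 12.3.1 and 12.3.2 in SAP section 10.
- State in the report that by-period columns confound regimen with calendar time and retention, and that changes from parent baseline include earlier treatment.
- Reconcile the protocol and SAP passages on entry regimen, so that the start of each period is unambiguous.

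The cost is SAP wording and programming: dose dates are already needed for exposure, and the protocol's AE listing already carries treatment at onset. The price is less exposure and less precise rates in the 200 mg columns. Because all 200 mg data fall early and much of the 100 mg data fall late among those who stayed, the new columns are not a clean dose comparison.

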### 8.7.1 Adverse events

Any AE that started in the parent study must be reported on the medical history form in this extension study. Only those events that start on/after enrollment into the extension study or are ongoing at the start of the extension study and become worse after or concurrently to extension study enrollment must be reported as AEs.

All AEs will be classified by Primary System Organ Class (SOC) and Preferred Term (PT) according to the most recently available version of the MedDRA dictionary.

In summaries by SOC and PT, adverse events will be sorted within each SOC and PT in alphabetical order. In summaries by PT, AEs will be sorted within each PT in alphabetical order.

Details for imputing missing or partial start dates of adverse events are described in [Section 7.2.2](#).

TEAEs are defined as any AEs occurring or worsening on or after the date of signing of the Informed Consent Form for the extension study. AE summary tables will be presented for TEAEs only and will include the following:

- All TEAEs
- Related TEAEs (AE will be defined as related if causality is possibly, probably, or certainly related)
- TEAEs by maximum severity

# Statistical Analysis Plan (SAP)

- TEAEs leading to study discontinuation
- Serious TEAEs
- TEAEs leading to death.

An overall summary for the categories above will be presented by treatment group and overall.

Due to the various durations of exposure to a treatment, the exposure-adjusted AE incidence rate (per 100 subject-years) will be summarized by treatment group. The incidence of AEs will be presented by system organ class and PT. In addition, all TEAEs will be summarized by SOC, PT and treatment group using frequency counts and percentages (i.e., number and percentage of subjects with an event).

Where a subject has the same adverse event, based on preferred terminology, reported multiple times in the study, the subject will only be counted once at the preferred terminology level in adverse event frequency tables.

Where a subject has multiple adverse events within the same system organ class in the study, the subject will only be counted once at the system organ class level in adverse event frequency tables.

When reporting adverse events by intensity, in addition to providing a summary table based on the event selection criteria detailed above, summary table will also be provided based on the most intense event - independent of relationship to study treatment.

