### **9.3.5      Investigational Medicinal Product Discontinuation**

Subjects may voluntarily discontinue IMP for any reason at any time, or completely withdraw from the study (see [Section 9.3.4](#)). Subjects who consent will undergo the EoT/Follow-up assessment approximately 4 weeks after administration of the last dose of IMP.

At any time during this long-term extension study, subjects not deriving sufficient clinical benefit in the opinion of the Investigator should be discontinued from IMP. Investigators should monitor the clinical benefit of each subject in an ongoing manner throughout the study in order to make the determination as to whether it is appropriate for them to continue to participate.

IMP must be discontinued under the following circumstances and further steps need to be discussed with the medical monitor:

- A serious adverse event (SAE), drug reaction or complication, or an unacceptable AE, whether attributed to IMP or not, that precludes continuation of treatment with IMP. This includes the development of allergic reactions or the development of other potentially serious drug reactions to medication required by the protocol,
- Diagnosis of malignancy (except basal or squamous cell carcinoma) during study (treatment may be continued at the discretion of the subject and Investigator, and in consultation with the medical monitor),
- Subjects who develop suicidal behavior ([Section 12.4](#)),
- Evidence of pregnancy,
- Withdrawal of informed consent,
- Lost to follow-up,
- Significant non-compliance of the subject with study procedures,
- Decision of the Sponsor to terminate the subject, site, or the study.

The derivation of clinical response (at Week 52 for the Phase 2 parent study) will be made within the IVRS system using information provided by the study site. The IVRS system will determine the subject's eligibility to continue into the long-term extension study. Subjects who fail to meet eligibility criteria at the end of their parent study will not be eligible to continue to the long-term extension study in accordance with the IVRS instruction, and would continue in the Follow-up period of their parent study.

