		
drug that had been given previously. This means that any other event is automatically excluded and can never qualify for 'Certain' (even in the case of a positive re-challenge observation).
 
5. It reappears on re-administration of the drug (only if ethically correct i.e. in case of non-serious and easily treatable AEs).

Abbreviations: AE(s) = adverse event(s).

The Investigator should consider the following, before reaching a decision on causality assessment:

- Time relationship between IMP intake and event's onset,
- De-challenge,
- Re-challenge,
- Medical history,
- IMP,
- Mechanism of action of IMP,
- Class effect,
- Concomitant treatments in use,
- Withdrawal of IMP,
- Lack of efficacy/worsening of existing condition,
- Erroneous treatment with IMP or concomitant medication,
- Protocol-related process.

Action taken with IMP due to the AE:

- None,
- Drug permanently discontinued,
- Drug temporarily discontinued,
- Unknown/not applicable.

Other action taken:

- Specific therapy/medication,
- Surgical medical procedure,

- (Prolonged) hospitalization.

Each single AE must be rated by choosing one of the following outcomes:

- Recovered/resolved,
- Recovering/resolving,
- Not recovered/not resolved,
- Recovered with sequelae/resolved with sequelae,
- Fatal,
- Unknown.

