# Statistical Analysis Plan (SAP)

- Subjects Screened
- Screen Failure(s)
- All Subjects as Treated (ASaT)

The number and percentage (based on ASaT) of subjects in each of the following disposition categories will be summarized overall and by treatment group:

- Completed treatment
- Prematurely discontinued the treatment and the reasons for discontinuation
- Completed study
- Prematurely discontinued the study and the reason for discontinuation

A listing will be provided for subjects who discontinued treatment or who discontinued study with reasons for discontinuation.

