# Statistical Analysis Plan (SAP)

laboratory results is to be reported as a non-serious AECI, using the terminology "accidental or intentional overdose without adverse effect."

2. An elevated AST or ALT laboratory value that is  $\geq 3 \times$  the ULN and an elevated total bilirubin laboratory value that is  $\geq 2 \times$  ULN and, at the same time, an alkaline phosphatase laboratory value that is  $< 2 \times$  ULN, as determined by way of protocol-specified laboratory testing or unscheduled laboratory testing, is to be reported as a non-serious AECI.
3. Infections that require IV antibiotics but do not meet the definition of an SAE will be designated a closely monitored AE for this study.
4. Depression and suicidal ideation and behavior events.

In addition, a listing containing individual subject adverse event data for TEAEs leading to discontinuation from study, Serious TEAEs, TEAEs leading to death, AESIs, and ECIs will be provided separately. All AEs, including pre- and post-treatment AEs, will be presented in an individual subject data listing.

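### SAP 8.7.1 summarises and separately lists AEs leading to study discontinuation, but gives AEs that ended treatment with IMP no table or listing of their own

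*SAP*

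**What the plan says.** SAP 8.7.1 introduces its tables with "AE summary tables will be presented for TEAEs only and will include the following" and names six categories: all TEAEs, related TEAEs, TEAEs by maximum severity, "TEAEs leading to study discontinuation", serious TEAEs and TEAEs leading to death. The same section promises a listing in which "TEAEs leading to discontinuation from study, Serious TEAEs, TEAEs leading to death, AESIs, and ECIs will be provided separately". Neither place names AEs that led to stopping IMP.

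SAP 8.3 treats the two kinds of exit as different outcomes. One disposition row is "Prematurely discontinued the treatment and the reasons for discontinuation" and another is "Prematurely discontinued the study and the reason for discontinuation".

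Protocol 9.3.5 draws the same line: "Subjects may voluntarily discontinue IMP for any reason at any time, or completely withdraw from the study". Its mandatory AE criterion is about the drug: an event "that precludes continuation of treatment with IMP". Protocol 11.1.1.9 has the site record the action taken with IMP because of the AE, and one of the options is "Drug permanently discontinued".

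**The concern.** The stopping rule in the protocol produces discontinuations of IMP, whereas the AE table in the SAP counts discontinuations from the study. A subject can stop IMP because of an AE, attend the EoT/Follow-up visit as asked, and be recorded as having finished the study or as having left it for another reason. That event then stays out of the one table meant to show AEs that led to discontinuation.

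Long-term safety is the primary objective, and a reader of the report will look to that table for tolerability. The sponsor uses the IMP-based measure itself: the background in Protocol 7.1 supports good tolerability in an earlier Phase 3 psoriasis study partly by a low incidence of AEs leading to discontinuation of IMP. As written, the SAP does not plan that measure here, so the extension could not be set directly beside the earlier programme on it.

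**Working it through.** No arithmetic applies. The documents give no rate of AE discontinuation, and no power was calculated. The check sets the provisions side by side.

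1. **Planned AE outputs (SAP 8.7.1).** Of the six summary categories, one concerns discontinuation, and it is tied to the study. The dedicated listing is tied to the study as well.

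2. **Are the two events distinct?** SAP 8.3 gives each its own row with reasons, and Protocol 9.3.5 names them as alternatives. Protocol 11.3.2 shows that the protocol can state both when it means both: a positive pregnancy test leads to stopping IMP and to withdrawal from the study.

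3. **What follows stopping IMP?** One EoT/Follow-up visit about four weeks after the last dose (Protocol 9.1.3.1.3, 9.3.5 and Table 9-1 note c) and a final ADA sample after 20 weeks from the last dose (Table 9-1 note j). No off-drug visit schedule is planned beyond that.

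4. **How is such a subject classified?** SAP 8.3 has a row for completing the study but does not define completion. The AE-level item in Protocol 11.1.1.8 asks whether the AE made the subject discontinue, without saying from what. Protocol 12.3.1 speaks only of withdrawal.

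5. **Consequence for a subject who permanently stops IMP because of an AE:**
   - coded as leaving the study for that AE: the event is in the SAP 8.7.1 table;
   - coded as completing the study after EoT/Follow-up: the event is not in that table;
   - coded as leaving the study for another reason: the event is not in that table.

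   In all three cases the event stays in the all-TEAE tables, and the treatment row of the disposition table counts the subject, provided AE is a recorded reason (the reason codes are not shown).

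6. **Range.** The share of treatment-ending AEs missing from the table runs from none (all coded the first way) to all (none coded that way). Nothing in the documents narrows it.

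7. **Can the missing table be built?** Yes. Action taken is collected for each AE (Protocol 11.1.1.9) and is meant for the full AE listing (Protocol 12.3.1).

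**The case against.** The strongest reply is that little or nothing is lost. With no off-drug visit schedule, stopping IMP is close to leaving the study, and the two sets probably overlap heavily. The disposition table and its listing already give the reasons for stopping treatment, by treatment group and overall. The events remain in the all-TEAE, severity and relatedness tables and in the exposure-adjusted rates, and the full AE listing shows action taken.

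The protocol also blurs the terms in places. Section 9.3.4, on withdrawal, asks the site to register discontinuation from IMP; 10.1.1 links missed doses to discontinuation from the study; and 11.1.1.1 speaks of subjects leaving the study because of an AE. The SAP's label may simply stand for the single discontinuation flag in 11.1.1.8. The table list need not be exhaustive, and SAP section 9 leaves the table templates to a separate document.

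Most of this stands, and it limits the weight of the point. It does not close the gap. A disposition row gives a count of subjects without SOC, PT, relatedness or severity, and a by-subject listing is not a summary. Uncertainty about what the flag means is itself a reason to define the category. An open list permits another table but does not commit the sponsor to one.

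A reader might infer that AEs ending treatment will be undercounted and tolerability made to look better. The documents do not support that: the result depends on eCRF coding they do not show, and the undercount could be zero. A reader might also apply an assumed discontinuation rate to the 286 subjects who could enrol. That would count assumed discontinuers out of a ceiling, not missed events, so no such figure is given. Nor would the gap bias a comparison, since the SAP plans no statistical tests and the study has no placebo comparator.

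**Conclusion.** The point holds as a minor gap in the planned tables. Two things follow from the text alone: AEs that ended treatment are not guaranteed a summary by SOC, PT and treatment group, and the study-discontinuation table may leave out subjects who stopped IMP for an AE without being coded as leaving the study for it.

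The size of any omission cannot be derived and may be small. The conclusion assumes that the label in SAP 8.7.1 means what it says. If the sponsor uses it for any AE that ended treatment, the remaining problem is wording. It is worth correcting because the field is already collected and the IMP-based measure is the one the sponsor cites from its earlier study.

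**What to change.** In SAP 8.7.1, add TEAEs leading to permanent discontinuation of IMP, defined as action taken equal to "Drug permanently discontinued". Include the category in the overall summary, in the tables by SOC and PT by treatment group and overall, and in the separate listing. Keep TEAEs leading to study discontinuation as a second line.

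One sentence in SAP 8.3 should also say how a subject who stops IMP and attends EoT/Follow-up is classified for study completion, so that the two lines can be read together.

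The cost is one extra table and listing. No new data collection and no change to the conduct of the study are needed.
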